### Funding

The study is made possible by Innlandet Hospital Trust (grant number 150406), the Dam Foundation, a Norwegian non-profit organisation (grants number ref 19-3656) and the Norwegian Cancer Society reference 247593001), the Liaison Committee for Education, Research and Innovation in Central Norway (grant number 19/4740-3), and The Joint Research Committee between St. Olav's hospital and the Faculty of Medicine and Health Sciences, NTNU – The Norwegian University of Science and Technology (FFU) (grant number 2018/42795 ).

---

 Further details, please see "references", open access paper: Røyset I et al. Geriatric assessment with management for older patients with cancer receiving radiotherapy. Protocol of a Norwegian cluster-randomised controlled pilot study. *J Geriatr Oncol.* 2022 Apr;13(3):363-373. doi: 10.1016/j.jgo.2021.11.001. Epub 2021 Nov 12

## Introduction

The current study addresses a major challenge to our health care systems, i.e. to provide good, effective and personalized health services to a large and rapidly increasing group of older cancer patient with complex needs (1).

The study is a randomised controlled pilot study for older cancer patients receiving radiotherapy (**RT**). It is designed to test the feasibility, potential effect and cost-effectiveness of an intervention aiming to improve function and quality of life (**QoL**), and thereby reduce the burden for the patients, their families and the society. The intervention program will be based on geriatric assessment with management, and comprises a targeted and personalised, primary health care based multicomponent intervention. In line with a proposal from the Norwegian Health Minister related to the new Norwegian cancer strategy (2), assigned municipal cancer nurses will serve as service coordinators to ensure a seamless treatment trajectory and a smooth transition of patients across sectors. The study will be conducted as a joint effort between specialists in geriatric and oncologic medicine as well as hospital and primary health care services, and represents the basis for a subsequent multicentre randomised trial (**RCT**).

The study is part of a larger project emerging from Innlandet Hospital Trust (SI) (Figure 1, page 2). Through this project, active collaboration is established between SI, St Olavs Hospital, 41 out 48 municipalities in Hedmark and Oppland counties and Trondheim municipality. Finances for one full-time and one part time (50%) project nurse are granted from SI. Furthermore, a 50% position for a project nurse for two years will be financed by grants from the Joint Research Committee between St. Olavs Hospital and the Faculty of Medicine and Health Sciences, NTNU. Running expenses will be covered by grants from the same committee, the Liaison Committee for Education, Research and Innovation in Central Norway and SI, jointly, and means to finance a PhD student connected to the pilot study are covered by grants from Extrastiftelsen.

## Background and current knowledge

Older cancer patients ( $\geq 65$  years) represent the majority of the cancer population, and their absolute number grows due to an aging population. In comparison to their younger counterparts, older cancer patients often present with a multiplicity of problems. They frequently suffer from somatic or psychiatric comorbidities, and are often frail with impairment in mobility, daily life functioning and cognition. When diagnosed with cancer and needs of therapy, these patients are at substantial risk of complications and functional decline (3-5). Thus, following cancer treatment, older patients have higher mortality and morbidity(6-8). Recovery also takes longer and may not always be achieved (5).

To avoid adverse outcomes that come at high personal and societal costs, and to ensure that optimal cancer treatment can be administered, a systematic assessment of the older patient's overall health status and potential vulnerability is necessary (9). This is particularly important considering the result of a recent study by our study group, demonstrating that oncologists are poorly trained to recognize frailty in their patients (10). Measures should thereafter be undertaken to improve existing deficits and prevent deterioration, and targeted rehabilitation procedures should be planned and implemented. Presently no such assessments or procedures are systematically applied in Norwegian cancer care.

**Geriatric assessment (GA)** addresses problems that are frequent in older age (3, 4) and includes systematic assessment of somatic health (such as comorbidity, medications, nutrition); mental health (such as cognition, anxiety and depression); functional aspects (such

as activities of daily living (ADL) and instrumental ADL (IADL) and physical function); and social network and living situation. GA is currently the best established method to identify older patients' vulnerability (11). Performed by an interdisciplinary geriatric team and followed by adequate management of identified vulnerabilities (GA with management), the approach has documented success in improving outcomes in non-cancer populations (12, 13).

During the last decades, GA has been adapted for cancer care, and mounting evidence shows that GA may identify remediable problems, affect oncological treatment decisions and predict survival or adverse effects from chemotherapy and cancer surgery (3, 14, 15). Despite this, and strong recommendations from current guidelines (3, 9, 16), GA has not been integrated into common oncology practice.(17) All GA domains cover problems that may negatively affect outcomes of cancer and cancer treatment (4). On the other side, these problems may also be prevented, alleviated or improved. For instance may treatment of comorbidities be optimised and inappropriately described medications withdrawn (4, 18). Interdisciplinary rehabilitation addressing physical activity and nutritional counselling may improve physical and nutritional deficits (19, 20). Mobility, independency and QoL are highly prioritized by older patients (21, 22). These outcomes are interconnected and may all be promoted by tailored physical exercise (23). GA with management (GAM) interventions are therefore strongly recommended to optimise treatment and care for older cancer patients (17).

[figure not shown]
Evidence for the potential benefits is lacking (17).

**Radiotherapy in cancer treatment:** RT is a main treatment modality in cancer, and may be used with curative or palliative intent. Short- and long-term side effects occur in both settings, and may be local, i.e. related to the involved organs, or general, e.g. fatigue and physical deterioration. Curative RT is conventionally given in higher total doses over a longer period of time, and have more frequent side effects compared to palliative treatment. There is evidence to suggest that older patients benefit from RT equally to younger patients (24, 25). However, high incidence of co-existing problems, higher toxicity rates, impaired QoL and physical deterioration are serious concerns (24, 25). Thus, using GA for both predictive and interventional purposes in older patients receiving RT has been advocated (24). To our knowledge, no studies on GAM interventions in this context have previously been published.

**The overarching research project:** The present pilot study is an essential part of a larger

project designed to develop, test and evaluate a cost effective, multicomponent, interdisciplinary treatment model for older cancer patients ( $\geq 65$  years) receiving RT. The project is designed in accordance with recommendations for development and evaluation of complex interventions (Fig 1) (26). To obtain sufficient knowledge to develop a feasible, targeted intervention, we have performed an observational study of older cancer patients ( $n = 301$ ) receiving RT to identify

**Figure 1. Design of the overarching project**

needs and problems (REK SØ-A 2016/2031). The study was closed for inclusion July 2018, and results of preliminary analyses are pending. Focus group interviews with relevant hospital

and primary health care professionals have been conducted (2017). Individual patient interviews to obtain detailed information about their perception of potential areas for improvement are running (REK SØ B 2018/1068). Experience, results and preliminary results from these studies represent the basis for the development of the intervention to be tested in the present pilot study.

**Rationale for a pilot study:** Before embarking on a larger multicenter RCT, the conduct of a pilot study is paramount. Although GAM has proven successful in other contexts (12, 13), there is no universally accepted recipe for how such an intervention should be performed and implemented. To be feasible and efficient, adjustments according to patient population, health care organization and available resources are necessary. A pilot study is needed to provide evidence for the feasibility from a patient as well as an organizational perspective. It is crucial to know if the intervention may be more relevant for some subgroups than others, to ensure that patients are able to adhere to all aspects of the intervention or if adjustments are needed, and to ensure that the intervention may be implemented within existing services and resources. A pilot study is also needed to enable adjustment of methods for evaluation and outcome assessment, and to enable precise sample size estimations for a future multicenter RCT.

## Study aims and objectives

The present PhD-project will be conducted to provide the evidence needed to implement a cost-effective GAM intervention for older cancer receiving RT on a larger scale, aiming at improving QoL and function and thereby reduce the burden for the patients, their families and the society.

### The detailed objectives are to:

1. assess the potential short- and long term effect of the intervention on global QoL and physical functioning for older cancer patients receiving RT
2. assess the feasibility of the intervention
  - a. at the patients' level (recruitment, compliance and adherence)
  - b. at the organizational level (structures facilitating or impeding implementation and collaboration across sectors and between professionals)
3. study the use of health care services and related costs in the intervention and control group

## Scientific significance and new knowledge that can be derived from the project

The present study will provide new knowledge on the needs of elderly cancer patients receiving RT, the feasibility of performing a multicomponent intervention based on collaboration across sectors and between disciplines, and on the potential benefits of GAM interventions on outcomes of particular relevance to older patients. Thus, the study will contribute to fill several knowledge gaps. Studies evaluating GAM interventions for cancer care are missing, and there is an urgent need to implement GA into routine clinical practice, and to establish the feasibility. Moreover, studies on older patients addressing treatment outcomes such as functioning and QoL are scarce, but highly advocated. The knowledge generated from the study will therefore be of major international interest, and essential for future planning of health services for an increasing number of patients with complex needs.

Furthermore, introducing GA to the hospital and primary health care services will increase awareness and knowledge on geriatric problems, and provide experience with assessments and interventions that are beneficial for older patients in general. Likewise, the study includes

[figure not shown]
collaboration with a range of municipalities of varying size and health care organization, and involves hospital with different level of expertise. Overall, the results will be broadly applicable for the management of older patients.

## Design, methodology and analyses

### The intervention

The intervention is developed by the interdisciplinary, experienced research group of this study in close collaboration with user representatives and hospital and primary health care professionals (reference group, page 12), and based on experience, results and preliminary results from the foregoing studies of the overarching project (Fig 1). Additionally, we have taken advantage of experience and results from another observational study by our study group “Cancer in the elderly; a prospective, observational study” (REK SØ C 2012/104) (10, 27) as well as studies evaluating GAM interventions in older, non-cancer patient conducted by members of our study group (12, 28, 29).

[figure not shown]
**Figure 2**  
GAM and included domains

According to results from a former study by our group(10), as well as preliminary data from the foregoing studies (Fig 1), evaluation of comorbidities and medications, appropriate treatment of depressive and somatic symptoms, nutritional counselling and physical rehabilitation will be important components of the intervention.

The intervention is a multicomponent GAM intervention (Fig 2) that will be adjusted to each patient's needs and capacity to comply. It focuses on somatic and mental health, function and social situation including living condition. Measures adapted to each patient will target these areas according to needs and deficits identified by a systematically applied GA.

**Figure 3. Intervention**

 Details on the intervention and intervention procedure were written in Norwegian in a protocol attachment and are to be found in the protocol paper: Røyset et al. Geriatric assessment with management for older patients with cancer receiving radiotherapy. Protocol of a Norwegian cluster-randomised controlled pilot study. JGO 2022

The initial GA and start of the intervention will be handled by the PhD student or project nurse before RT commences. Pre-planned guidelines will be followed, and contribution from relevant hospital professionals will be sought according to needs. Then the intervention will be offered in the primary health care taking advantage of existing services, e.g. home care, meal delivery, rehabilitation services, exercise groups etc.

A coordinating nurse will follow the patients with regular contact throughout RT and to end of intervention and 8 weeks post-RT. In Hedmark and Oppland this task will be assigned to those who are “cancer co-ordinators” or have a dedicated role as a “contact nurse” for cancer patients in their municipality. Repeated assessments will be performed by the end of RT and after 4 weeks to ensure that the intervention is properly adjusted to changing need (see also Fig 4).

Before recruitment of patients to this pilot study starts, seminars will be arranged for information and training of involved primary health care professionals. Through the foregoing observational study (Fig 1), the relevant nurses in the SI catchment area are all extensively familiar with GA.

## **Setting**

---

The primary study center is the Radiotherapy Unit (RTU) at SI providing RT to the population in Oppland and Hedmark counties (380 000 inhabitants), and treating about 700 patients per year, 2/3 are  $\geq 65$  years. Palliative RT represents about 60 % of the patients, and is administered independent of diagnosis. Curative treatment is given to breast, prostate, lung and skin cancers only. Hedmark and Oppland comprise 48 municipalities, and 30 of these have consented to participate in the present study. The RTU, St Olavs hospital, Trondheim will be the second study center. This RTU provides all RT services to the inhabitants in the catchment area including Trondheim municipality (180 000 inhabitants). RT is administered to about 250 patients  $\geq 65$  years from Trondheim per year. The municipality of Trondheim is organized into 4 health care districts.

## **Design**

---

[figure not shown]
The present study is a controlled cluster-randomized pilot study. Cluster-randomization is chosen to avoid contamination of the control group. It is paramount that control and intervention patients are not handled by the same primary health care professionals, and this can only be achieved by randomizing municipalities (or health care districts).

Before patient recruitment commences, a selection of 32 municipalities/city districts (= clusters) will be stratified into blocks in accordance with number of inhabitants. The selection will include city districts, large and smaller municipalities to ensure sample size and representativity. Clusters within each block will be randomly assigned to one of the groups by using a computer-generated code, 16 in each group.

Eligible patients from clusters assigned to intervention will enter the intervention group and enter the intervention program. Patients from control clusters will enter the control group.

These patients will receive treatment and care in accordance with usual routines and standards

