**Figure 4. Study design**

\* PROMs (patient reported outcome measures): will also be applied in both groups at end RT and at end RT + 4 weeks

Consenting, eligible patients will be included when admitted to planning of RT. Baseline assessments will be performed by a project nurse/the PhD student at start of RT. As we believe that the intervention may have both a short- and long term impact on patients' QoL and functioning, the patients will be followed for 52 weeks with specific study assessments and for survival up to 5 years. The main outcomes assessments will take place at 8 and 16 weeks after the end of RT. A blinded assessor will be used to assess outcomes other than those that are patient reported (**PROMs**) at these time points.

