## Patients

Patients will be consecutively recruited at the RTU, Gjøvik and St. Olavs hospital.

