### The exclusion criteria are

- severely ill with a life expectancy < 3months
- referred to receive one fraction of RT only (one day treatment)

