## **Conclusion:**

We aim at including a total of 186 patients, i.e. 24 patients more than originally estimated. It also means that more patients than preplanned will have to be included from some of the participating municipalities, i.e. from those that during the inclusion period present with eligible patients.

For the analysis of the primary outcome, however, we need at least 138 evaluable patients, i.e. patients where the primary outcome is registered. Thus, by closely monitoring the inclusion and response rate, it may be possible to stop the enrolment before the end of Sep 2020, and before we reach 186 patients. We may also need to enroll more than the estimated 186 patients to reach the target number of evaluable patients, and in this case, a new application to the Ethical Review Board will be submitted.

**To be noted:** Due to the increase in sample size, the inclusion period was extended primarily to Sep 2020. However, study recruitment had to be paused in March 2020 due to the covid pandemic, and was thereafter opened again in the autumn 2020, please see published protocol paper .

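### The baseline physical function score can be recorded after the arm is known and the intervention has started, and no by-arm record of eligible versus included patients is planned

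*Protocol*

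**What the plan says.** **Allocation comes first.** Protocol, Design: "Before patient recruitment commences, a selection of 32 municipalities/city districts" are stratified by population, and "Clusters within each block will be randomly assigned to one of the groups by using a computer-generated code, 16 in each group". The arm then follows from residence: "Eligible patients from clusters assigned to intervention will enter the intervention group and enter the intervention program". Living in a participating municipality is itself an inclusion criterion.

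**Enrolment comes later.** Protocol, Figure 4 text: "Consenting, eligible patients will be included when admitted to planning of RT". Protocol, Patients, gives the place and manner: "Patients will be consecutively recruited at the RTU, Gjøvik and St. Olavs hospital". No role is named for identifying patients or taking consent. Some criteria need judgement, such as the exclusion of patients who are "severely ill with a life expectancy < 3months" and the requirement to be able to complete questionnaires.

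**Intervention start and baseline.** Protocol, Figure 3 text: "The initial GA and start of the intervention will be handled by the PhD student or project nurse before RT commences". The Figure 4 text gives the baseline assessment to the same two roles, at the start of radiotherapy. The amendment of 29-02-20 replaced a limit of treatment day 2 with day 3 (fewer than 15 fractions) or day 6 (15 or more).

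**Analysis.** The primary outcome is QLQ-C30 physical function, which is patient reported, so the blinded assessor does not cover it. The SAP's Primary analysis uses a linear mixed model with baseline value, time and time by group, and random effects for patients within clusters. The protocol's Statistics section adds further covariate adjustment without naming the covariates.

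**The concern.** When clusters are allocated before patients are identified, randomisation protects the choice of clusters but not the choice of patients within them. If those who consent differ by arm, the comparison carries a prognostic difference that population-size blocking cannot remove. The usual partial defence is to adjust for a baseline measured before anyone could react to allocation. Here the timing weakens that defence: the covariate may be recorded once staff, and possibly the patient, know the arm and after the intervention has begun.

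The second line of defence is to be able to see differential recruitment if it happens. That needs counts and characteristics of eligible and included patients by arm, and neither document plans them, although recruitment is a stated feasibility objective and the pilot is meant to inform a larger trial.

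**Working it through.** No figure in the plan is challenged, so there is none to reproduce. The check is one of sequence, followed by illustrations of sensitivity.

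**1. Order of events**
- Cluster randomisation: before recruitment (Protocol, Design).
- Inclusion: at radiotherapy planning (Figure 4 text).
- Initial geriatric assessment and intervention start: before radiotherapy, by PhD student or project nurse (Figure 3 text).
- Baseline: start of radiotherapy, same roles (Figure 4 text), allowed up to day 3 or day 6 (amendment of 29-02-20).

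As written, intervention start precedes baseline, and nothing requires the questionnaire to come first. The amendment justifies the wider window by noting that radiotherapy's own adverse effects come late in treatment. It does not address the intervention already being under way.

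**2. What a contaminated baseline does**
Inputs from the SAP, Sample size: baseline to follow-up correlation 0.5, SD 24 per group. Assuming equal SDs at the two times, the adjustment slope is about 0.5 × 24/24 = 0.5. If early effects or expectations shift the intervention arm's baseline by s points, the adjusted difference moves by about −0.5 × s:
- s = +2: −0.5 × 2 = −1 point.
- s = +4: −0.5 × 4 = −2 points, or 2/12 = 17% of the 12-point target.

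A downward shift moves the result the other way. With a true 12-point effect and the SE of 4.08 derived in step 3, losing 2 points lowers power from 83.6% to 68.8%. The values of s are assumed.

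**3. What residual selection does**
Two standard errors bracket the plan:
- From 80% power for 12 points: SE = 12 / (1.96 + 0.84) ≈ 4.28.
- From the SAP inputs with Amendment B's 69 evaluable patients per arm, ICC 0.10 and 16 equal clusters per arm: SE = 24 × √(1 − 0.5²) × √(1 + (69/16 − 1) × 0.10) × √(2/69) = 4.08.

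For an assumed residual prognostic difference b, type I error = P(|Z + b/SE| > 1.96):

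| b (points) | SE 4.28 | SE 4.08 |
|---|---|---|
| 0 | 5.0% | 5.0% |
| 2 | 7.5% | 7.8% |
| 3 | 10.8% | 11.4% |
| 4 | 15.4% | 16.5% |

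**4. Whether the recruitment fraction can be derived**
Protocol, Setting: about 700 × 2/3 ≈ 467 patients aged 65 or over per year at the first unit and about 250 at the second, 717 in all. The original target of 162 in one year is 162/717 = 23%, and 186 would be 26%. The denominator includes non-participating municipalities and ineligible patients, so the true fraction is higher and unknown. It cannot be obtained by arm at all, which is what a log would supply.

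**The case against.** Several stronger readings are tempting, and the documents do not support them.

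- **That the staff who deliver the intervention also recruit.** No section names who identifies or consents patients. Shared roles are documented only for baseline assessment and intervention start. More than one project nurse post is funded, so the roles need not be one person, and primary care delivers most of the programme.
- **That recruiters worked to quotas and could pick patients.** Amendment B gives preplanned numbers of 2 to 16, never called caps. Its Conclusion says "more patients than preplanned will have to be included from some of the participating municipalities", but the same sentence ties this to municipalities where eligible patients appear. How these numbers fit with consecutive recruitment deserves a sentence of clarification. It is not evidence of discretion.
- **That information and consent were not neutral between arms.** Consent pages and the Norwegian attachments were not available, so nothing can be concluded about them.
- **That eligibility could simply be assessed blind to municipality.** Residence is an eligibility criterion, and not every municipality takes part.
- **That every remedy is free of staffing cost.** The documents do not say so, and a separate masked recruiter might well need resources.

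The plan also has real safeguards: consecutive recruitment, blocking by population, baseline adjustment, a blinded assessor for performance tests, and a stated reason for cluster allocation (contamination). What they leave open is the timing of the one named covariate and the absence of by-arm recruitment data. The fair practical objection is that the February 2020 amendment reports time pressure around baseline registrations. That argues for moving only the questionnaire.

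**Conclusion.** The point stands in a limited form and is worth acting on. Allocation precedes identification of patients, residence reveals the arm, recruiter masking is not described, and no by-arm account of eligible and included patients is planned. The plan allows the baseline physical function score to be recorded after the arm is known and the intervention has begun, so adjusting for it may neither remove selection nor leave the treatment effect intact.

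The size is unknown. The type I error figures and the power loss rest on assumed values of b and s, a normal approximation and, for the SE of 4.08, 16 equal clusters per arm. Amendment B reports that one municipality withdrew and four others had enrolled nobody, so fewer clusters may contribute. The figures show sensitivity. A reader might infer that the trial is biased, but the documents give no evidence that it is.

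**What to change.** **Baseline timing** (Protocol, Figure 4 text and the February 2020 amendment on baseline registrations). State that in both arms the baseline QLQ-C30 is completed by the patient at inclusion, at radiotherapy planning, after consent but before the arm is disclosed to the patient and before the initial geriatric assessment. The performance tests may keep the amended window.

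**Screening log** (Protocol, Patients). State who recruits. At both radiotherapy units, log every patient who meets the criteria, by arm, with age, radiotherapy intent and reason not included. Report the recruitment fraction and these characteristics by arm.

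**If recruitment is already complete.** Build the by-arm account from existing unit records as far as they allow, and check the primary result against the date of the baseline form relative to intervention start.

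**Cost.** One questionnaire is handled somewhat earlier, in a setting where the amendment reports time constraints, and the two units keep an extra log. The SAP's Primary analysis counts eight weeks from baseline while its opening paragraph counts from the end of radiotherapy, so the visit anchor should be settled in the same edit.
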